#### **9.2.3 Suspected unexpected serious adverse reactions (SUSARs)**

N/A

#### **9.3 Annual safety report**

N/A

#### **9.4 Follow-up of adverse events**

All AEs will be followed until they have abated, or until a stable situation has been reached. Depending on the event, follow up may require additional tests or medical procedures as indicated, and/or referral to the general physician or a medical specialist. SAEs need to be reported until end of study within the Netherlands, as defined in the protocol.

### **9.5 Data Safety Monitoring Board (DSMB) / Safety Committee**

The establishment of a Data Safety Monitoring Board or Safety Committee is not deemed necessary for this study. The study aims to investigate a potentially safer treatment method than the current standard of care. It is unlikely that the risk of adverse events will be increased in the experimental cohort compared to the standard cohort. The only difference between the two cohorts is the fractionation schedule. The only difference is expected in the rate of local control and radionecrosis, which constitutes the primary study endpoint.

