As clinicians, we observe an increasing number of long term survivors over several years with brain metastases. Brain necrosis or radionecrosis is a long term side effect of SRT which occurs in +/-20% of patients and the incidence may increase up to +/-40% if SRT is combined with immunotherapy. Radionecrosis may cause neurologic symptoms, such as focal neurological deficits, neurocognitive dysfunction and seizures, which require treatment with steroids, bevacizumab, or sometimes even surgery. SRT is mostly delivered with an ablative high radiotherapy dose in a single fraction. In the first millimeters close to the brain metastasis, the healthy brain tissue receives a high dose as well.

In radiotherapy literature, it is known that more fractionated radiotherapy, e.g. hypofractionated radiotherapy (fSRT), may decrease side effects. fSRT means delivering the ablative dose in multiple fractions (f.e. 5 fractions) over several days instead of delivering the ablative dose within half an hour. Recent retrospective studies showed that risk difference of local failure and radionecrosis is almost 30% in larger tumors (>2.5 cm; constituting around

50% of metastases), while the incidence is equivalent in smaller metastases. To achieve a local control of more than 90% after one year, it is important to deliver a cumulative biologically effective dose (BED) of at least 50 Gy. 35 Gy in 5 fractions results in a BED of more than 50Gy. Another potential benefit of fSRT over SRT in one or three fractions is better induction of an abscopal effect. SRT in one or three fractions results in massive tumor necrosis. fSRT may result in more regulated cell death: apoptosis, with better antigen presentation of dying tumor cells. It is hypothesized that this may subsequently result in better activation of the immune cells against the cancer and better control of micrometastases outside the irradiation field. Several studies are ongoing in which SRT is combined with immunotherapy to increase systemic tumor control and thereby improve survival.

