### 8.3.3 Fractionation schedule and radiation dose before SRT

Patients randomized into the experimental fSRT cohort receive a fractionation schedule based on "Working Agreement for uniform dose prescription stereotactic (LINAC) irradiation of brain metastases, Dutch Platform of Neuro Oncology". This is 35 Gy in five fractions, or 30 Gy in five fractions if the metastasis is situated in the brainstem.

Patients randomized into the standard cohort will receive a fractionation schedule based on "Working Agreement for uniform dose prescription stereotactic (LINAC) irradiation of brain metastases, Dutch Platform of Neuro Oncology". This is in the range of 15 Gy in a single fraction up to a 24 Gy in three fractions.

The dose gradient outside the PTV will be as steep as possible to spare healthy brain tissue. Within the PTV there will be considerable dose inhomogeneity

*Dose prescription to brain metastases*

PTV of brain metastases	Dose 1 fraction	BM in brainstem (GTV=PTV)	Dose 5 fractions (Gy)	BM in brainstem (GTV=PTV)
<1 cm 	24	16	35	30
1-10 cm 	21	16	35	30
10-20 cm 	18	16	35	30
20-65 cm 	15 or 3X8Gy	No SRS	35	30

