### **8.7 Premature termination of the study**

The aim of the study is to investigate a different and possibly safer treatment method than the current standard of care. The study is based on the radiotherapy concept of fractionating the treatment. When the total dose of radiation is divided into several, smaller doses over a period of several days, there are fewer toxic effects on healthy cells. Therefore, the risk of adverse events in the experimental cohort is unlikely to be greater than in the standard cohort and premature termination of the study is not likely.

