#### 9.2.2 Serious adverse events (SAEs)

A serious adverse event is any untoward medical occurrence or effect that

- results in death;
- is life threatening (at the time of the event);
- requires hospitalization or prolongation of existing inpatients' hospitalization;
- results in persistent or significant disability or incapacity;
- is a congenital anomaly or birth defect; or
- any other important medical event that did not result in any of the outcomes listed above due to medical or surgical intervention but could have been based upon appropriate judgement by the investigator.

An elective hospital admission will not be considered as a serious adverse event.

The investigator shall report serious adverse events to [[contact]](mailto:[contact]) without undue delay after obtaining knowledge of the events, unless, for certain serious adverse events, the protocol provides that no immediate reporting is required.

Adverse experiences of a serious and unexpected nature, whether or not related to the cerebral radiotherapy, must be reported immediately. Adverse events that are

unexpected, should be reported if there is a possibility that it could be related to the administration of the radiotherapy.

The investigator will report all SAEs to the sponsor without undue delay after obtaining knowledge of the events, except for the following SAEs: epilepsy, deterioration of existing neurologic impairment after the radiotherapy, alopecia, fatigue, headache, and taste disorders.

The sponsor will report the unexpected SAEs through the web portal *ToetsingOnline* to the accredited METC that approved the protocol, within 7 days of first knowledge for SAEs that result in death or are life threatening followed by a period of maximum of 8 days to complete the initial preliminary report. All other unexpected SAEs will be reported within a period of maximum 15 days after the sponsor has first knowledge of the serious adverse events.

Patients with brain metastases generally have a poor life expectancy of around 3-12 months. Therefore, a significant proportion of patients is expected to die within the study duration of 1 year after SRT.

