#### **10.4 Interim analysis**

See paragraph 8.7.

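### The safety-oversight argument treats the experimental arm as the same dose divided, but the dose table also changes total dose, and BED is higher than standard in the largest lesions

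*Protocol*

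**What the plan says.** Section 9.5: "The establishment of a Data Safety Monitoring Board or Safety Committee is not deemed necessary for this study". Among the reasons given is that "The only difference between the two cohorts is the fractionation schedule".

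Section 8.7 starts from a radiobiological principle: "When the total dose of radiation is divided into several, smaller doses over a period of several days, there are fewer toxic effects on healthy" tissue. It then infers that adverse-event risk in the experimental arm should not exceed that in the standard arm, and that "premature termination of the study is not likely". Section 10.4, on interim analysis, reads in full "See paragraph 8.7", and 8.7 describes no interim look.

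Section 8.3.3 sets the doses. For the experimental arm: "This is 35 Gy in five fractions, or 30 Gy in five fractions if the metastasis is situated in the brainstem". For the standard arm the table steps down with PTV: 24, 21 and 18 Gy in one fraction, then 15 Gy in one fraction or 3x8 Gy at 20-65 cm3.

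Section 9.2.2 requires prompt SAE reporting to the sponsor, "except for the following SAEs: epilepsy, deterioration of existing neurologic impairment after the radiotherapy" and four further items. It then puts expected SAEs in a half-yearly line listing. Severe neurologic impairment and epilepsy appear there only as consequences of intracranial progression. Section 1 names seizures and focal deficits among the symptoms of radionecrosis.

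**The concern.** The argument in 8.7 works if a fixed total dose is split into smaller parts. If the total dose rises at the same time, the principle no longer settles which arm carries the greater risk to normal tissue. The protocol's Summary itself ties necrosis to lesion size and delivered dose, so the largest lesions are where the argument most needs to hold.

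Two things are at stake. First, the ethics committee is given a reason for light oversight (no safety board, no interim look, annual safety report not applicable) that the dose table does not bear out in one size band. Second, the routine that remains has a gap. A seizure or a worsening deficit caused by radionecrosis is exempt from prompt reporting, and the listing as worded does not capture it either. No breakdown by arm is specified.

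**Working it through.** **Inputs.** Doses and fraction numbers come from the table in section 8.3.3 (non-brainstem columns). The alpha/beta ratio, written x, is not given in the protocol. Values of 2, 3 and 10 Gy are assumed below, and the main result is also shown for every x > 0. BED is a fair yardstick because section 1 argues from it: "it is important to deliver a cumulative biologically effective dose (BED) of at least 50 Gy".

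**Formula.** For n fractions of d Gy, BED = n·d·(1 + d/x).

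**The protocol's own figure.** Section 1 says 35 Gy in five fractions gives a BED above 50 Gy. With 5x7 Gy, BED = 35 + 245/x. At x = 10 this is 35 + 24.5 = 59.5 Gy. It exceeds 50 Gy whenever x < 245/15 = 16.3. The figure reproduces.

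**All bands.**

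| PTV band | Regimen | BED formula | x = 2 | x = 3 | x = 10 |
|---|---|---|---|---|---|
| every band | 5x7 (experimental) | 35 + 245/x | 157.5 | 116.7 | 59.5 |
| <1 cm3 | 1x24 | 24 + 576/x | 312.0 | 216.0 | 81.6 |
| 1-10 cm3 | 1x21 | 21 + 441/x | 241.5 | 168.0 | 65.1 |
| 10-20 cm3 | 1x18 | 18 + 324/x | 180.0 | 126.0 | 50.4 |
| 20-65 cm3 | 1x15 | 15 + 225/x | 127.5 | 90.0 | 37.5 |
| 20-65 cm3 | 3x8 | 24 + 192/x | 120.0 | 88.0 | 43.2 |

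**20-65 cm3.** Experimental minus standard:
- against 1x15: (35 - 15) + (245 - 225)/x = 20 + 20/x
- against 3x8: (35 - 24) + (245 - 192)/x = 11 + 53/x

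Both are positive for every x > 0, so the ordering does not depend on the assumed ratio. Relative excess over 1x15 and 3x8:
- x = 2: 157.5/127.5 and 157.5/120.0, or 24% and 31%
- x = 3: 116.7/90.0 and 116.7/88.0, or 30% and 33%
- x = 10: 59.5/37.5 and 59.5/43.2, or 59% and 38%

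**10-20 cm3.** The difference is 17 - 79/x, zero at x = 79/17 = 4.6. The experimental BED is lower at x = 3 (116.7 against 126.0) and higher at x = 10 (59.5 against 50.4).

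**Below 10 cm3.** Against 1x21 the crossover is x = 196/14 = 14; against 1x24 it is 331/11 = 30. At ratios 2 to 10 the experimental BED is lower.

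**Reporting route for a serious seizure or neurological deterioration.** If caused by cancer progression: exempt from prompt reporting, but severe impairment and epilepsy appear in the half-yearly listing. If caused by radionecrosis: still within the exemption when recorded as epilepsy or as deterioration of an existing impairment, and not among the events described for the listing.

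**The case against.** Several objections have weight.

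- *The wording of 9.5.* Section 8.3.3 itself uses the term fractionation schedule to cover total dose as well as number of fractions. Read that way, the sentence in 9.5 is loose rather than false, and 9.5 goes on to say that radionecrosis and local control are expected to differ. This stands. The argument in 8.7 is the one that fits the table badly, since its conclusion is drawn directly from dividing the total dose.
- *Higher BED is not more necrosis.* A reader might infer that the experimental arm is more harmful in large lesions. The documents do not support that. The Summary and section 1 cite retrospective data in which fractionated treatment gave less local failure and radionecrosis, especially in larger tumours. Only the reasoning offered in 8.7 fails.
- *Other safeguards.* Both arms follow the same national working agreement, organ constraints are set per schedule, and section 11.4 calls both treatments accepted. A reader might also infer that early termination has been waived, or that excess necrosis would stay hidden until the final analysis. Neither follows. Sections 9.1 and 12.5 keep a halt and a premature end available. The trial is open label, MRI and toxicity are recorded every three months, and radionecrosis itself is not on the exemption list. What remains is that no tabulation by arm is specified.
- *Attribution.* One might say that a difference could not be credited to fractionation alone. That is true, but the objectives already compare regimens of five fractions with one or three, so this needs no separate correction.
- *Sparse cells.* If 130 patients were spread evenly over two arms and four bands, each cell would hold 130/8, or about 16. Section 1 cites a guideline limit of 20 cm3 per metastasis, so the top band may hold fewer; the protocol gives no share. The listing would therefore be for inspection, not for testing.

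**Conclusion.** The concern holds in a limited form. Total dose changes together with fraction number, so the divided-dose argument of 8.7, echoed in 9.5, does not support the safety conclusion for non-brainstem lesions with PTV 20-65 cm3. There the experimental BED is higher than both standard options at any alpha/beta ratio. The size of the excess (24-33% at ratios 2-3, 38-59% at 10) rests on the linear-quadratic formula and assumed ratios; its direction within that formula does not depend on the ratio. The result must not be extended to smaller lesions, where the direction depends on the ratio (10-20 cm3) or reverses at ratios 2 to 10 (below 10 cm3).

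The reporting gap in 9.2.2 rests on the text alone: symptoms that section 1 links to radionecrosis can miss both reporting routes. None of this shows that the experimental arm is less safe or that a safety board is required.

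**What to change.** 1. Reconcile sections 8.7 and 9.5 with the table in 8.3.3. State that total dose differs between the arms as well as the number of fractions, and that the BED comparison varies by PTV band. If the case for light oversight is kept, rest it on grounds that survive this, such as the cited retrospective data and the common working agreement.
2. In section 9.2.2, have the existing half-yearly line listing include every radionecrosis, epilepsy and neurological-deterioration SAE whatever its attributed cause, with treatment arm and PTV band shown. Table 1 already records the PTV of the largest metastasis, so a band can be assigned without new data.

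The cost is some protocol wording and a few columns in a listing already produced. The downside is that the sponsor sees safety counts by arm during the trial; because the trial is already open label, that is a modest price. No dose, stopping rule or safety board is proposed.

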## 10. STATISTICAL ANALYSIS

### 10.1 Primary study parameter(s)

Differences in the composite endpoint (either radionecrosis or local failure) at 2 years post-radiotherapy are calculated as a percentage in each cohort. The binomial test will be used to compare the percentage between the two cohorts.

Summary tables for continuous variables will include the following statistics: mean, standard deviation. Summary tables for categorical variables will include: N, proportion.

If the data is normally distributed, the means will be compared using independent samples Student's T-Tests. In case of violation of the normality assumptions, non-parametric tests will be used. Proportions will be compared by using Chi-square testing. Unless otherwise indicated, tests will be 2-sided.

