## 8. METHODS

### 8.1 Study parameters/endpoints

#### 8.1.1 Main study parameter/endpoint

Incidence of adverse local event (ALE) at 2 years post-radiotherapy with respect to baseline.

Definition of ALE = either radionecrosis or local failure according to Response Assessment in Neuro-Oncology Brain Metastases (RANO-BM).

Definition of radionecrosis = increasing size and low perfusion MR by interpretation of a dedicated radiologist (multidisciplinary board).

Definition of local failure is  $\geq 20\%$  increase in sum longest distance relative to nadir in target lesion.

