**Figure 1: Study flow chart**

**Table 1 Study parameter summary table**

	Baseline	End of RT	Months post (f)SRT								
			3M	6M	9M	12M	15M	18M	21M	24M	
Standard clinical care:											
Clinical characteristics: year of birth, gender, primary tumor type, presence of extracranial visceral metastases, primary tumor control, date diagnosis primary tumor, type of systemic therapy	X										
Coded data (see paragraph 12.1): patient number in electronic patient dossier											
Planning MRI & CT: number of brain metastases, total volume of brain metastases, volume of largest brain metastases	X										
Treatment characteristics: GTV largest metastasis, PTV largest metastasis, total volume GTV of all metastases, and total volume PTV of all metastases. Maximum dose in the PTV in anymetastasis. Maximum dose brain stem, chiasm, and optic nerves		X									
Physical examination	X										
WHO-PS and/or KPS	X										
Standard follow-up:											
Follow-up MRI: adverse local event (either radionecrosis or local failure according to RANO), distant brain recurrences			X	X	X	X	X	X	X	X	
Toxicity (CTCAE v5.0)			X	X	X	X	X	X	X	X	
Not part of standard follow-up:											
HRQoL (EORTC QLQ-C30, QLQ-BN20)	X		X	X		X		X		X	
IADL ( EQ-5D 5L)	X		X	X		X		X		X	
Other follow-up:											
Use of dexamethasone or bevacizumab	X		X	X	X	X	X	X	X	X	
Use of AED	X		X	X	X	X	X	X	X	X	
Salvage treatment, type of salvage treatment, date of salvage treatment						X					X
Alive/dead			X	X	X	X	X	X	X	X	
Symptomatic radionecrosis or local failure			X	X	X	X	X	X	X	X	

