### **8.5 Replacement of individual subjects after withdrawal**

With respect to patients applicable for this study willing to participate, and who have signed informed consent (paragraph 11.2): before randomization any patient will be replaced if the patient withdraws for any reason. These patients are not included in the statistical analysis. After the randomization, patients withdrawing for any reason will not be substituted by additional patients and these patients are analyzed by intention to treat.

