### **8.6 Follow-up of subjects withdrawn from treatment**

Patients who withdraw after randomization will not be requested to participate for follow-up questionnaires. Patients are asked if it is allowed to consult their medical chart for treatment characteristics and survival length.

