### 10.2 Secondary study parameter(s)

Secondary study parameters (as listed in paragraph 8.1.2, including facultative endpoints such as HRQoL and neurocognition) will be presented per cohort. Due to the presence of repeated measurements mixed modelling will be used to analyze use of anti-epileptica, dexamethasone and bevacizumab, IADL and to investigate the effect of fSRT on quality of life.

Overall survival (from date of first radiotherapy until death) will be estimated by using Kaplan-Meier methodology. To assess whether there is difference between survival in the groups, the Log-rank test will be used. To investigate the effect of prognostic factors on survival, a Cox regression model will be used. To estimate the cumulative incidence of adverse local events (ALE), a competing risk model with death as a competing risk will be estimated. Fine and Gray's test will be employed to assess the difference between cumulative incidence in the two cohorts. Cause specific hazard Cox model will be employed to investigate the effect of prognostic factors on the cumulative incidence of ALE.

Care will be taken to minimize missing data and to continue to follow up those who withdraw from the study. To account for non-compliance and protocol deviation the analysis will be performed based on the intention to treat concept.

All analyses concerning the competing risk model will be performed in R environment by using the library mstate and cprisk. All other analyses will be performed in SPSS version 26.0 (IBM Corp, Armonk, NY).

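### The primary 2-year ALE percentage is sound only with complete ALE follow-up, which section 8.6 does not secure, while the estimate that allows for losses is ranked secondary

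*Protocol*

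**What the plan says.** - **Endpoint.** Protocol section 8.1.1: "Incidence of adverse local event (ALE) at 2 years post-radiotherapy with respect to baseline".
- **Primary analysis.** Section 10.1: "Differences in the composite endpoint (either radionecrosis or local failure) at 2 years post-radiotherapy are calculated as a percentage in each cohort". The percentages are compared with what it calls a binomial test. The section does not say how an ALE-free death, or a patient whose ALE status becomes unknown, is counted.
- **Withdrawals in the analysis.** Section 8.5, for the period after randomization: "patients withdrawing for any reason will not be substituted by additional patients and these patients are analyzed by intention to treat". Section 10.2 likewise says that "the analysis will be performed based on the intention to treat concept".
- **Data after withdrawal.** Section 8.6: "Patients are asked if it is allowed to consult their medical chart for treatment characteristics and survival length". Section 10.2 says instead: "Care will be taken to minimize missing data and to continue to follow up those who withdraw from the study".
- **Source of ALE status.** Table 1, under standard follow-up, every three months: "Follow-up MRI: adverse local event (either radionecrosis or local failure according to RANO), distant brain recurrences".
- **Competing-risk estimate.** Section 10.2, for the cumulative incidence of ALE: "a competing risk model with death as a competing risk will be estimated". Section 2 lists this as a secondary objective.
- **Expected survival and allowance.** Section 9.2.2 gives a life expectancy of around 3-12 months. Section 4.4 raises the sample from 118 to 130 for missing data.

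**The concern.** A crude percentage needs a known outcome for every patient in its denominator. Deaths alone do no harm: an ALE-free death is a known outcome, and counting it as a non-event gives the cumulative incidence. Patients who leave follow-up alive are the difficulty. Under intention to treat they stay in the denominator, but section 8.6 seeks no ALE information on them, so in practice they would be counted as ALE-free from the day they leave. That lowers both percentages and shifts the difference if withdrawal differs between the open-label arms.

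The losses may also be related to the endpoint. Section 8.4 handles patients who become incapacitated and can no longer have MRI by the same withdrawal rules, and section 1 says that radionecrosis may cause focal deficits and neurocognitive dysfunction.

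Sections 8.6 and 10.2 cannot both be followed as written. A later analysis plan cannot recover data for which permission was not sought.

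**Working it through.** **1. The plan's own figure.** Section 4.4 uses 30% vs 10%, 59 per arm and a two-sided pooled Z test with exact binomial power. Exact enumeration gives power 0.8051, and actual alpha 0.0507 at a common rate of 10%. Both match. With 65 per arm (130/2) and the same rates, power is 0.832.

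**2. When the percentage equals the cumulative incidence.** Section 3 plans two years of follow-up for all, so only losses cause censoring. Without losses, the competing-risk estimate at 2 years is simply the number with ALE divided by the number randomized. That is the percentage of section 10.1 with ALE-free deaths as non-events. With losses, the two differ.

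**3. Does section 8.6 cover ALE?** It names two items. Table 1 uses the term treatment characteristics for target volumes and doses recorded at the end of radiotherapy. ALE stands in a separate row, under follow-up MRI. So ALE status is not among the data sought.

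**4. Size of the bias.** Assumptions: constant, independent hazards; 30% and 10% are 1-year risks while alive; survival is equal in both arms. Section 9.2.2 gives 3-12 months without saying whether this is a median. The main case takes a 12-month median. Withdrawal rates of 10% and 20% over 2 years (absent ALE or death) are assumed, since the protocol gives none.

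- ALE hazard per year: l = -ln(0.7) = 0.357 and -ln(0.9) = 0.105
- Death hazard: m = ln 2 = 0.693 at 12 months
- Withdrawal hazard: w = -ln(1-q)/2, that is 0.053 for q = 10% and 0.112 for q = 20%
- ALE observed by 2 years = l/(l+m+w) × (1 - exp(-2(l+m+w)))

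Complete follow-up, standard arm: 0.3567/1.0498 × (1 - 0.1225) = 0.298. Experimental arm: 0.1054/0.7985 × (1 - 0.2025) = 0.105.

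| Withdrawal, standard / experimental | Standard | Experimental | Difference (points) |
|---|---|---|---|
| none | 29.8% | 10.5% | 19.3 |
| 10% / 10% | 28.8% | 10.1% | 18.7 |
| 20% / 20% | 27.7% | 9.7% | 18.0 |
| 20% / 10% | 27.7% | 10.1% | 17.6 |
| 10% / 20% | 28.8% | 9.7% | 19.1 |

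The difference falls by 0.2 to 1.7 points. Because many patients die or have ALE first, 10% withdrawal means that about 4% and 5% of randomized patients are actually lost.

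Other survival assumptions, 10% withdrawal in both arms: at a 6-month median, 19.3% vs 6.5% instead of 19.8% vs 6.7%. At 24 months, which lies outside the protocol's range, 36.8% vs 13.3% instead of 38.3% vs 13.9%.

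**5. ALE-free deaths by 2 years**, with w = 0: m/(l+m) × (1 - exp(-2(l+m))) gives 58% vs 69% at a 12-month median and 77% vs 88% at 6 months.

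**6. Power**, approximated by the exact two-proportion test with 65 per arm and complete follow-up: 0.799 at 12 months (29.8% vs 10.5%) and 0.610 at 6 months (19.8% vs 6.7%).

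**The case against.** **The plan does provide for losses.** Section 4.4 adds 10% for missing data, 8.5 keeps withdrawals in the analysis, and 10.2 promises to limit missing data. This stands in part: it would be wrong to say that losses are ignored. But the 10% enlarges the sample and does not classify outcomes, and the promise in 10.2 is not carried through in 8.6.

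**A 2-year proportion is a legitimate primary measure.** It matches the sample-size calculation, and the competing-risk estimate is already prespecified. This also stands. Deaths as non-events is the likely reading, on which the two measures agree apart from losses, and the gap is small. The case for changing the rank is that the better estimate is already planned and costs almost nothing.

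**Outcome classification may be left to an analysis plan.** Fair. The mere absence of a sentence on ALE-free deaths is not the point here. The choice of primary measure and the conflict between 8.6 and 10.2 are fixed in the protocol itself.

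**Competing-risk methods are no cure.** Censoring at the last MRI assumes non-informative loss, which is doubtful if neurological decline drives withdrawal. This stands, and it is why seeking ALE status after withdrawal comes first among the changes. Moreover, a test of whole curves, such as the one named in 10.2, does not address a fixed 2-year difference.

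**A stronger reading to resist.** With so many ALE-free deaths, a reader might infer that they would be dropped. In the 12-month scenario that would give 71% vs 34% on about 27 and 20 of 65 patients. No section proposes this, and the wording on incidence and intention to treat points the other way. It should not be used as the size of the problem.

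**Conclusion.** The point holds in limited form and should be fixed. The primary percentage is a valid 2-year incidence if ALE-free deaths count as non-events and ALE follow-up is complete. Section 8.6 works against the second condition and conflicts with 8.5 and 10.2.

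The likely bias is modest: a difference of 17.6 to 19.1 points instead of 19.3 in the scenarios with 12-month median survival. This rests on constant independent hazards, equal survival, the 1-year reading of 30% and 10%, and assumed withdrawal of 10-20%. Loss related to ALE is not modelled and could make the bias larger. The documents do not support a claim that the primary result is invalid or that deaths will be excluded.

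**What to change.** 1. **Section 8.6.** Bring it into line with 10.2: after withdrawal, with the patient's consent, seek ALE status from standard follow-up MRI as well as treatment characteristics and survival.
2. **Section 10.1.** Make the primary estimate the 2-year cumulative incidence of ALE in all randomized patients, with death as a competing event and patients lost to ALE follow-up censored at their last MRI. Report the 2-year difference with a 95% CI and a two-sided 5% test of that same fixed-time difference. Keep the whole-curve test of 10.2 as supportive.
3. **Sensitivity analysis.** Report the percentage of all randomized patients with ALE, with ALE-free deaths as non-events, compared by the pooled Z test of section 4.4.

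**Cost.** Text changes in 8.6, 10.1 and 10.2, and a change to the consent question on chart data. No added imaging or enrolment is needed: the MRI is standard care and the cumulative incidence is already planned. The non-informative-loss assumption must be stated. Power must be restated as approximate, about 80% at 12-month and 61% at 6-month median survival with 65 per arm. That restatement applies equally to the present percentage with deaths as non-events.
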